9. EFFICACY ANALYSES

a. Primary Efficacy Analysis

All summary statistics will be produced in accordance with section 8, and all primary efficacy analyses will use the ITT population. All tests will be two-sided and use a Type I error of 0.05. First, we will test for a main effect of incentive versus no incentive using an independent proportions Z-test. If this main effect is significant, we will proceed to study the two messaging factors using only data from individuals randomized to the incentive condition with higher response rate. If the main effect of incentive is not significant, we will proceed with studying the two messaging factors using all data and assuming incentive level does not interact with messaging or have any other effect on the outcome. Next, using either half or all the data, we will model the binary indicator of complete survey response or non-complete survey response within 7 days using a logistic regression. The model will adjust for race and sex and will incorporate 5 indicators of treatment arm (3 introductory messaging levels x 2 tobacco use messaging levels – 1 reference group). We will compute the marginal response probability for each arm, averaging over the observed distribution of sex and race. Standard errors and 95% confidence intervals will be obtained for each marginal response probability using the delta method. If one of the confidence intervals has a lower limit that exceeds the upper limit of all the others, its corresponding set of factor levels will be used in the primary study, pending confirmation that exploratory analyses do not raise red flags about disparities in response rates. If a set of confidence intervals have lower limits that surpass the upper limits of the other intervals, the final choice of factor levels to use will be based on discussions amongst the study team and key stakeholder, taking into consideration the point estimate, confidence interval length, and exploratory data on disparities.

i. Secondary Analyses of Primary Efficacy Endpoint

We will conduct secondary analyses of the primary efficacy endpoint using the per protocol, instead of the ITT population, to assess if documented engagement after receipt of the full intervention affected efficacy.

ii. Analyses of Secondary Endpoints

We will conduct similar analysis outlined in Section 9a to assess the effect of the interventions on the secondary outcome, partial completion of the survey.

b. Exploratory Efficacy Analyses

We will conduct exploratory efficacy analyses within each of the following pre-specified subgroups: 1) females vs non-females and 2) Black adults vs non-Black adults (using EHR data). We conduct primary and secondary efficacy analysis within each of these subgroups in accordance with section 9a and 9b above. The summary statistics will be produced in accordance with section 8. This subgroup analysis is justified because there are existing disparities in LCS guidelines in each of these groups and we aim to understand if our strategies may help to reduce or increase disparities before implementing them broadly.

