4. STUDY OBJECTIVES AND ENDPOINTS

a. Study Objectives

The primary objective of this analysis is to assess how the combination of different messaging content and incentives impact response rates to the survey.

b. Endpoints

The primary endpoint is full completion of the survey defined as responding to all three survey questions within 7 days of initial outreach. The secondary endpoint is partial completion of the survey (defined as responding to at least one survey question within 7 days of initial outreach).

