6. SAMPLE SIZE

To determine the sample size for the trial, we considered a range of hypothesized response rates from 3% to 12% for the 12 arms representing different combinations of messaging and incentives and based on prior research studies. We hypothesized this range of response rates would be plausible for many of the arms and chose the final sample size based on our ability to distinguish statistically two arms towards the extremes of the range. Figure 1 below shows a plot of the 95% confidence intervals for the range of hypothesized response rates (plotted on both x- and left y-axes). With N=6,000 participants total (500 per arm), we would be able to detect a 5-percentage point difference between two arms if one of the arms had a response rate of 3% to approximately 7%. In comparison, with N=3,600 we would only be able to detect a 5-percentage point difference between two arms if one of the arms had a response rate of 3% or lower. Although larger samples would allow us to detect smaller differences, piloting on a larger sample would decrease the number of participants available for future trials. Balancing this logistical concern with power to detect differences between arms, we chose to include N=6,000 participants in this pilot study.

[figure not shown]

Figure 1: Illustration of 95% confidence interval length for potential response rates between 3% and 12%. Response rates are plotted on both the x- and y-axes. Each panel plots confidence intervals for the total sample size (N) given on the right y-axis.

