The primary analysis model will adjust for race and sex. Since both these variables must be present in the EHR for randomization, there will be no individuals excluded due to missing race or sex in the analysis. There may however be participants in the dataset that have “unknown” race documented in the EHR. For randomization, these individuals are classified as “Non-Black” adults. For summary statistics, these individuals will be reported as unknown race. Due to the large number of patients to be randomized (N=500 per arm), we expect randomization to provide balance on all baseline covariates and therefore will not adjust for any other variables in the models. By definition, there will be no missing primary or secondary outcomes.

e. Multiple Testing

[figure not shown]
Since we are aiming to identify the best combination of factor levels, we are more concerned with making Type II errors than Type I errors. Therefore, we will not adjust for multiple testing.

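### SAP 9.a reduces the 12-arm factorial to six message cells after one incentive test, so no model estimates an incentive-by-message interaction or all 12 combinations; a supporting 12-arm model would fill the gap

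*SAP*

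**What the plan says.** SAP section 4.a sets the primary objective: to "assess how the combination of different messaging content and incentives impact response rates to the survey". Section 7.e declines a multiplicity adjustment on the ground "Since we are aiming to identify the best combination of factor levels". Section 6 chooses the sample size on "our ability to distinguish statistically two arms towards the extremes of the range", and states: "With N=6,000 participants total (500 per arm), we would be able to detect a 5-percentage point difference between two arms", provided the lower rate is between 3% and roughly 7%.

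Section 9.a then works in two steps.

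- **Step 1.** A Z-test compares incentive with no incentive.
- **Step 2, test significant.** "we will proceed to study the two messaging factors using only data from individuals randomized to the incentive condition with higher response rate".
- **Step 2, test not significant.** All data are used, "assuming incentive level does not interact with messaging or have any other effect on the outcome".

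In both cases the logistic model adjusts for race and sex and "will incorporate 5 indicators of treatment arm", which is one fewer than the six introductory-by-tobacco message cells. It has no incentive term. If one cell's confidence interval lies wholly above the rest, "its corresponding set of factor levels will be used in the primary study", subject to a check on disparities. If a set of cells stands apart, the team and stakeholders decide.

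The secondary-endpoint and subgroup analyses reuse this scheme, and the per-protocol analysis changes only the population. Section 8 provides summary tables with a column per intervention. These could show all 12 arm rates, but only descriptively.

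**The concern.** The question asked and the analysis planned do not match. The objective and the aim concern combinations that include incentive, and the sample size is a calculation about arms of 500. The model never holds more than six cells and never contains both incentive and message.

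Each branch leaves its own gap.

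- **Not significant.** The pooled cells are averages over incentive levels, so no single combination is estimated. Failing to reject a main effect does not show that it is zero, and it says nothing about interaction: opposite effects under two messages cancel in the main effect. The chosen pair reaches the later study without an incentive level, and the SAP gives no rule for setting one.
- **Significant.** The six retained cells are six real combinations with a named incentive level. The other six are never modelled, so nothing in the model would show that the best combination lies among them.

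At stake is which message and incentive combination goes into the later primary study, and whether the trial can report how incentive and message act together.

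**Working it through.** **Inputs from the documents.** Twelve arms of 500 (3,000 per incentive level); two-sided alpha of 0.05; hypothesized arm rates of 3% to 12%; N=3,600 (300 per arm) as the rejected alternative. The documents give no expected incentive effect or interaction, so every rate pattern below is my assumption within 3% to 12%. Race and sex are taken to have no effect.

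**1. The plan's own figure.** Two 95% intervals stop overlapping at a 5-point difference when 1.96 × [√(p(1−p)/n) + √((p+0.05)(0.95−p)/n)] ≤ 0.05.

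- n=500: the left side is 0.0387 at p=3%, 0.0500 at p=6.66% and 0.0508 at p=7%. The limit is about 6.7%, where the SAP says approximately 7%.
- n=300: the left side is 0.0500 at p=3%, matching the SAP's 3%.

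The figure reproduces. It is a calculation about single arms of the 12-arm design, whereas section 9.a analyses six cells of 500 or six pooled cells of 1,000.

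**2. How often a real average incentive effect is treated as zero.** Power ≈ Φ[(|d| − 1.96·SE₀)/SE₁], with 3,000 per level.

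- 7% vs 8%: SE₀ = SE₁ = 0.0068, so (0.0100 − 0.0133)/0.0068 = −0.49. Power is 31%; not significant in 69%.
- 7% vs 9%: power 81%; not significant in 19%.
- 7% vs 10%: power 99%; not significant in 1%.

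The test is adequate for average effects of about 3 points or more. The weakness lies in small effects and in effects that differ by message.

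**3. Crossover.** Let incentive give 10% with three message pairs and 5% with the other three, and no incentive the reverse. Both halves average (3×10 + 3×5)/6 = 7.5%, so the test is non-significant in about 95% of trials. Every pooled cell is (10 + 5)/2 = 7.5%, so the 10% combinations cannot be seen.

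**4. Best combination in the half set aside.** Let all incentive arms be 8%, and the no-incentive arms 12% once and 5% five times.

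- The no-incentive mean is (12 + 5×5)/6 = 6.17%, so the difference is 1.83 points.
- With SE₀ = 0.00662 and SE₁ = 0.00660, (0.01833 − 0.01298)/0.00660 = 0.81. Power is 79%.
- In those 79% of trials the half holding the 12% arm is not modelled.
- With the other five no-incentive arms at 6%, the mean is 7.0% and the share falls to about 31%.

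**5. What a 12-arm model could show at the same N.** For incentive by introductory message there are 1,000 participants per cell. A 2-degree-of-freedom Wald test on risk differences, for introductory messages A/B/C without and then with incentive, has power of:

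- 42% for 7/7/7% vs 10/7/7% (noncentrality 4.09);
- 84% for 7/7/7% vs 12/7/7% (noncentrality 10.60).

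At rates near 8%, the 95% half-width of an interaction contrast is 1.96 × √(4×0.08×0.92/n). That is ±3.4 points between two introductory messages (n=1,000) and ±2.7 points for the tobacco message (n=1,500). A single arm has 1.96 × √(0.08×0.92/500) = ±2.4 points.

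**The case against.** The sequence and its assumption are stated openly in advance, and settling the incentive before choosing the message is a recognizable selection strategy. Pooling to 1,000 per cell fits a team that fears Type II error more than Type I. The Protocol (Methods 3) calls this part exploratory and secondary, the SAP calls it a pilot, each choice awaits a disparities check, and arm rates may be visible in the summary tables. All of this stands and limits the weight of the point. It does not supply an interaction estimate, or a rule for the incentive level after a non-significant test.

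Two stronger readings are tempting.

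**That the incentive test should be dropped and the selection rule applied to all 12 arms.** I simulated 200,000 trials per case with additive effects: one message pair +5 points, and incentive +1, +2 or +3 on a base of 6%, 5% or 4%. Under the plan, 89%, 41% and 1% of single winners carry no incentive level. Under a 12-arm rule that falls back on six incentive-averaged pairs, 99%, 97% and 93% of winners come from the fallback, which fixes no incentive level either. The 12 intervals alone name a winner in about 1%, 2% and 6% of trials. Where the incentive clearly works, the plan settles its level by a pre-specified test, and that is worth keeping.

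**That the SAP expects one arm to stand 5 points above 11 equal arms.** Section 6 speaks only of two arms toward the ends of a range. The single-arm pattern is a stress case: with one incentive arm at 8% vs 3%, 10% vs 5% or 12% vs 7% for the rest, the test is non-significant in about 57%, 70% and 77%. Nor can a pooled interval be faulted for missing a single arm's rate, since it estimates a message pair.

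**Conclusion.** The gap is real and can be read directly from the text: no planned model estimates an incentive-by-message interaction or all 12 combinations, and the non-significant branch rests on an assumption that its test cannot support. The sample size figure itself is correct. The introductory-by-tobacco interaction is covered, since the five indicators saturate the six message cells. The significant branch gives valid estimates for six named combinations.

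The size depends on assumed rates: about 69% of trials treat a 7% vs 8% effect as zero, about 95% pass over a 5-point crossover, and up to about 79% set aside the better half in the constructed pattern of step 4. Nothing in the documents says that such patterns are expected. I would class this as a cheap improvement, minor to moderate. A reader should not infer that the planned selection is invalid.

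**What to change.** Keep the incentive test and the existing selection rule, and amend section 9 as follows.

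1. **Supporting analysis, whatever the test result.** Fit one logistic model on all randomized participants, with 11 arm indicators plus race and sex. Report with 95% confidence intervals the 12 marginal probabilities, the incentive effect averaged over message pairs, and the incentive-by-introductory and incentive-by-tobacco-message interactions.
2. **Test not significant.** Replace the sentence assuming no interaction and no other incentive effect. Say that message pairs are reported as averages over incentive levels, and that the incentive level carried forward is settled under 9.a's team-discussion rule, using the averaged incentive effect, the interaction intervals and the 12 arm estimates.
3. **Test significant.** Before the choice is final, check the 12 arm estimates for a better combination in the other half.
4. **Subgroups (clarification only).** The test could go different ways in a subgroup and its complement, so state that both sides of a disparity comparison use the same arms.

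The cost is SAP wording and slightly more analysis, with no extra participants. Power for small interactions stays limited, about 42% for 7/7/7% vs 10/7/7%, and the SAP should say so. The interaction test should not become a second gate.

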3. INTRODUCTION

a. Preface

Despite growing evidence that lung cancer screening (LCS) reduces lung cancer-specific mortality, LCS across the United States and at Penn Medicine is remarkably low (Fedewa et al. 2022). This is due in part to challenges with identifying adults who meet eligibility criteria for lifetime smoking intensity (i.e., 20 pack-years or greater), which is often missing from the electronic medical record. We developed a simplified tool (using yes/no questions) that has been shown to estimate pack-year eligibility accurately (Rendle et al. 2023). In this study, we aim to test the impact of different strategies (i.e., introductory and norming messages and incentives) on survey response rates when the survey is delivered via text message.

b. Scope of the analyses

These analyses will compare the effect of three different factors (introductory messages, norming messages, and incentives) on survey response rates using a 3x2x2 factorial design.

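### SAP 9.a plans no factor-level contrast or test for either message factor, and its interval-separation rule would miss most message effects of 2 to 3 points

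*SAP*

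**What the plan says.** SAP section 3.b (Scope of the analyses) sets the task: "These analyses will compare the effect of three different factors (introductory messages, norming messages, and incentives) on survey response rates using a 3x2x2 factorial design". Section 4.a words the primary objective differently, as being to "assess how the combination of different messaging content and incentives impact response rates to the survey".

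Section 9.a (Primary Efficacy Analysis) works in two steps.

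- The incentive is tested as a main effect with a two-proportion Z-test.
- The messages are then studied either in the better incentive level only (if that test is significant) or in all participants (if not). The logistic model adjusts for race and sex and "will incorporate 5 indicators of treatment arm (3 introductory messaging levels x 2 tobacco use messaging levels", less one for the reference. Its planned outputs are six marginal response probabilities, each with a delta-method 95% interval.

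A combination is chosen if its interval lies wholly above all the others. If a set of intervals lies above the rest, the team chooses with stakeholders. Nothing is laid down for the case where neither happens.

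Sections 9.a.i, 9.a.ii and 9.b apply the same method to another population, endpoint or subgroup. Section 7.e gives the error priority: "Since we are aiming to identify the best combination of factor levels, we are more concerned with making Type II errors than Type I errors".

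**The concern.** A factorial design lets each factor be assessed on the whole analysed sample, averaged over the other factors. Section 9.a uses that for the incentive but not for the messages. It plans no contrast, odds ratio, risk difference or test for the introductory message, the tobacco-use message or their interaction, and no later section supplies one.

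The selection rule also works against a simple main effect. If one introductory message is better, two of the six cells share the gain. If one tobacco-use message is better, three do. Those cells have the same true rate, so a single winner is nearly out of reach. To show the factor cleanly, every interval at the better level must clear every other interval: 2 × 4 = 8 pairs for the introductory message, 3 × 3 = 9 for the tobacco-use message.

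At stake is the choice of message for the next phase. For modest effects the likely result is no separation, and the SAP then gives no basis for choosing.

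**Working it through.** **Inputs.** SAP section 6: 6,000 participants, 500 per arm, rates of 3% to 12%. Section 9.a: two-sided 5% tests and individual 95% intervals. Cell sizes follow: 3,000 / 6 = 500 if one incentive level is kept, 6,000 / 6 = 1,000 if both are pooled. Message effects are my assumption: gains of 2 to 5 points over a base of 3%, 5% or 7%, inside the SAP's range.

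**The SAP's own figure.** Section 6 says: "With N=6,000 participants total (500 per arm), we would be able to detect a 5-percentage point difference between two arms", with the lower arm at 3% to about 7%. This reproduces as non-overlap of two expected intervals:

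1.96√(p(1−p)/n) + 1.96√((p+0.05)(0.95−p)/n) ≤ 0.05

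- n = 500: holds up to p = 6.7% (2.19 + 2.82 ≈ 5.0 points).
- n = 300 (N = 3,600): holds up to p = 3.0% (1.93 + 3.07 = 5.00 points). This also agrees with the SAP.

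This is a statement about expected intervals, not power. For 7% against 12% at 500 per arm, a Z-test has 77% power, while the two intervals separate in about 48% of trials.

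**Precision near an 8% rate**, with SE of a difference = √(2 × 0.08 × 0.92 / n):

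- Tobacco-use factor, 3,000 per level: 0.70 points. A 5% test needs an observed gap of 1.96 × 0.70 = 1.37 points.
- Two cells of 1,000: SE 1.21. Non-overlap needs 2 × 1.96 × √(0.0736/1000) = 3.36 points, for that one pair.
- Two cells of 500: SE 1.72. Non-overlap needs 2 × 1.96 × √(0.0736/500) = 4.76 points.

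**Simulation.** Six binomial cells with Wald 95% intervals; without covariates these equal the delta-method intervals of the saturated logistic model. The rule is credited with any separated set of one to five cells. The comparators, on the same data, are a 2-df chi-square for the introductory message (one of three messages better) and a Z-test for the tobacco-use message. The table is for a 5% base with only the named factor active. Each entry is introductory / tobacco-use.

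| Gain | Rule, 500 per cell | Test, 500 | Rule, 1,000 per cell | Test, 1,000 |
|---|---|---|---|---|
| 2 points | 0.2% / 0.2% | 49% / 64% | 0.5% / 0.3% | 81% / 91% |
| 3 points | 0.7% / 0.4% | 83% / 92% | 6.6% / 5.1% | 98.5% / 99.7% |
| 4 points | 3.3% / 2.4% | 97% / 99% | 33% / 29% | about 100% |
| 5 points | 14% / 11% | over 99% | 72% / 69% | about 100% |

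Across bases of 3%, 5% and 7%:

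- **2 to 3 points:** the rule separates in under 7%, except 19–23% for 3 points at a 3% base with 1,000 per cell. Test power runs from 39% (introductory message, 7% base, 2 points, 500 per cell) to over 99%.
- **4 points:** about 1–12% with 500 per cell, 14–68% with 1,000.
- **5 points:** 5–36% with 500 per cell, 45–94% with 1,000. Test power is over 98%.
- **Single-winner rule alone:** under 1% in every one of these scenarios.

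If both factors add 3 points to a 5% base, some set separates in 3.7% (500) or 21% (1,000) of trials. The introductory and tobacco-use tests then have 75% and 88% power (500), or 96% and 99.5% (1,000).

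**The case against.** The best defence is that 9.a is a selection procedure. Sections 4.a and 7.e aim at the best combination, section 6 sizes the trial on telling two arms apart, and a cell-level model suits that aim. Where one cell alone stands out the rule does better: 5% against 10% separates in 26% (500 per cell) or 80% (1,000) of trials, and 3% against 12% in 99% or more. The point estimates remain informative too. With one tobacco-use message at 7% and the other at 9%, the highest of the six estimates carries the better message in 94% (500) or 99% (1,000) of trials. For one better introductory message the figures are 85% and 95%. All this stands and supports keeping the six-cell table. But 9.a does not say to choose by point estimate when nothing separates, and 3.b still promises a comparison of factors.

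Four stronger readings are tempting but not supported.

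- *The message factors are never estimated.* Five indicators for a 3 × 2 layout form a saturated model, so the factor contrasts can be derived from it. What is missing is a plan to do so.
- *A real message effect is almost always missed.* That fits most 2 to 3 point effects, and 4 points at 500 per cell. It does not fit the SAP's own 5-point difference at 1,000 per cell.
- *The trial cannot answer its question.* The mismatch is with 3.b; the objective in 4.a is about combinations.
- *Messages would be reported as indistinguishable.* The SAP draws no conclusion when intervals overlap.

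**Conclusion.** The point holds as a planning gap that should be fixed, not one that invalidates the trial. Section 9.a provides no factor-level contrast or test for two of the three factors named in 3.b. Its separation rule is also far less sensitive to a message main effect than tests on the same data. The loss is near total for most 2 to 3 point effects. At 5 points it is still large with 500 per cell, and moderate to small with 1,000. That is the reverse of the priority in section 7.e.

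Severity is limited by the setting. The protocol (Method for Assigning Subjects to Groups) treats the message testing as exploratory and subordinate to the main aims, and SAP section 6 calls the trial a pilot.

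The figures assume message effects that the documents do not give, effects that add on the percentage-point scale, equal cells, and no race or sex adjustment, which should matter little under stratified randomization. Each data branch is taken as given.

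**What to change.** In SAP 9.a, after the incentive step and on whichever data set the plan then uses for the messages (half or all), add:

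1. a 2-df test for the introductory message, a 1-df test for the tobacco-use message and the 2-df interaction between them;
2. marginal risk differences with 95% confidence intervals for each message factor, adjusted for race and sex;
3. where both incentive levels are pooled, incentive as a term in the model, with the incentive-by-message interactions reported;
4. a statement that these estimates are used alongside the six-cell table when choosing the combination, including when no interval or set of intervals separates.

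Keep the six-cell probabilities. Agree the text before outcomes by arm are seen, so that the contrasts are not post hoc.

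The cost is SAP wording and a few more model outputs, with no new data. The downside is that main-effect estimates assume the messages act roughly additively, and the interaction test has limited power. The six-cell table therefore stays as a check.
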